8.7 CRP

Table 14.2.7.1 summarizes CRP (standard test, not high sensitivity-hsCRP) at Screening and at Days 7, 14 and 29 and changes from Screening.

8.8 Subgroup Analysis

As noted in Section 5.6, the following variables will define subgroups.

- Stage 2 and Stage 3 AKI
- Acuity of AKI (i.e., whether or not AKI is diagnosed at time of presentation of abdominal infection or surgically confirmed NSTI, or during the 48 hours from the suspected diagnosis of abdominal infection or surgical confirmation of NSTI; developed AKI up to <24 hours or 25 to 48 hours after the suspected diagnosis of abdominal infection or surgical confirmation of NSTI)
- AKI diagnosed via creatinine criteria vs. urine output criteria
- Abdominal infection or NSTI
- Age ≥ 18 to ≤ 75 and >75 to ≤ 85 years old
- Baseline APACHE II ≥ 10 and < 10
- Cardiovascular failure yes and no
- Respiratory failure yes and no
- Gender male and female
- Caucasian and other
- BMI category (<30 , $30-40$, >40)
- Day 14 mSOFA ≤ 1 and Day 14 mSOFA ≥ 2
- Selected baseline pathogen type

The following tables will be provided for each subgroup. Results for the primary endpoint will be summarized in a forest plot.

14.2.1.1	Numbers and Percentages of Subjects Achieving Freedom from Durable Loss of Renal Function and Improvement in Durable Loss of Renal Function at Day 28 Using LOCF
----------	--

	ITT Analysis Set
14.2.2.1	Numbers and Percentages of Subjects Achieving Secondary Freedom from or Improvement in Durable Loss of Renal Function Endpoints at Days 14, 28, and 90 ITT Analysis Set

9 Presentation of Safety Evaluations

9.1 Adverse Events

Treatment-emergent AEs (TEAE) reported during the study will be summarized by treatment group according to Medical Dictionary for Regulatory Activities (MedDRA) System Organ Class (SOC) and Preferred Term (PT). Incidence rates of TEAE will be tabulated by class. The distributions of severity will be provided for drug-related AEs, separately by treatment group. Further tabulations by relationship and severity of AE may be provided.

9.1.1 Summary of adverse events

All analyses of adverse events will be based on the As Treated (Safety) Analysis Set. A summary of the numbers and percentages of patients within each treatment group experiencing at least one TEAE will be provided in Table 14.3.1.1. TEAEs will be defined as an AE occurring from Day 1 to end of study which is defined as Day 28. 'Drug-related' is defined as 'possibly', 'probably', or 'definitely' caused by the study medication.

The AE endpoints summarized in this table are:

- With one or more TEAE
- With one or more drug-related TEAE
- With one or more serious TEAEs
- With one or more serious drug-related TEAE
- With one or more severe TEAE
- With one or more moderate or severe TEAE
- TEAE with outcome of death
- TEAE with outcome of drug related death
- Discontinued study drug due to AE/SAE
- Discontinued from study due to AE/SAE

9.1.2 Specific adverse events

The incidence rates (%) and event counts of TEAEs by system organ class (SOC) and by preferred term (PT) will be summarized by treatment group in Table 14.3.1.2. This table will be organized so that SOCs are reported in upper case letters and PT's are reported in lowercase.

Table 14.3.1.3 will summarize the incidence rates (%) of specific TEAE PTs, sorted by descending incidence of PT in the active drug group.

The incidence rates (%) and event counts of drug-related TEAEs by SOC and by PT will be summarized by treatment group in Table 14.3.1.4.

The incidence rates (%) and event counts of serious drug-related TEAEs by SOC and by PT will be summarized by treatment group in Table 14.3.1.5.

Table 14.3.1.6 will summarize the incidence rates (%) of serious TEAE PTs, sorted by descending incidence of PT in the active drug group.

The incidence rates (%) and event counts of serious drug-related TEAEs by SOC and by PT will be summarized by treatment group in Table 14.3.1.7.

9.1.3 Severity of adverse events

The incidence rates (%) and event counts of severe TEAEs by SOC and by PT will be summarized by treatment group in Table 14.3.1.8.

Table 14.3.1.9 will summarize the incidence rates (%) of severe TEAE PTs, sorted by descending incidence of PT in the active drug group.

Counts of drug-related TEAEs in the active drug group will be summarized by severity, SOC and PT in Table 14.3.1.10. Similarly, counts of drug-related TEAEs in the placebo group will be summarized by severity, SOC and PT in Table 14.3.1.11.

9.1.4 Day 0 Adverse Events

A listing will be provided contain any events that occur prior to drug administration.

9.1.5 Safety listings

The following listings will be provided for all patients in the Safety Analysis Set. Adverse event listings will include SOC, PT, relationship, severity, onset and resolution dates, and action taken.

		AE Listings
1	16.2.7.1	All TEAEs Sorted by Specific AE: Day1+ by Treatment Group, Sorted by SOC and PT As Treated (Safety) Analysis Set
2	16.2.7.2	All TEAEs Sorted by Specific AE: Day1+ by Treatment Group, Sorted by Patient ID and Onset As Treated (Safety) Analysis Set
3	16.2.7.3	Drug-Related TEAEs Sorted by Specific AE: Day1+ by Treatment Group, Sorted by SOC and PT As Treated (Safety) Analysis Set
4	16.2.7.4	Serious TEAEs Sorted by Specific AE: Day1+ by Treatment Group, Sorted by SOC and PT As Treated (Safety) Analysis Set
5	16.2.7.5	Serious Drug-Related TEAEs Sorted by Specific AE: Day1+ by Treatment Group, Sorted by SOC and PT As Treated (Safety) Analysis Set
6	16.2.7.6	All TEAEs with Outcome of Death Sorted by Specific AE: Day1+ by Treatment Group, Sorted by SOC and PT As Treated (Safety) Analysis Set
7	16.2.7.7	All TEAEs with Outcome of Drug-Related Death Sorted by Specific AE: Day1+ by Treatment Group, Sorted by SOC and PT As Treated (Safety) Analysis Set

		AE Listings
8	16.2.7.8	All TEAEs with Outcome of Study Drug Discontinuation Sorted by Treatment Group, SOC, and PT As Treated (Safety) Analysis Set
9	16.2.7.9	All TEAEs with Outcome of Discontinuation from Study Sorted by Treatment Group, SOC, and PT As Treated (Safety) Analysis Set

9.2 Clinical Laboratory Assessments

9.2.1 Blood Chemistry

Table 14.3.2.1 summarizes the values and changes from screening (baseline) for each of 15 tests included in the chemistry panels at Screening, Day 7 and Day 14.

Table 14.3.2.2 provides a shift table summarizing the numbers and percentages of patients going from a normal blood chemistry value to a normal, low or high value at Day 7; going from a low baseline blood chemistry value to normal, low or high at Day 7; and going from a high baseline blood chemistry value to normal, low or high at Day 7. The percentages presented in this table correspond to each baseline status. For example, the one of the reported percentages will indicate the percentage of subjects that started with a normal value but ended with a high value. This will be done separately for each treatment group.

Table 14.3.2.3 provides the same information but for shifts to Day 14.

Table 14.3.2.4 provides a summary of blood chemistry frequencies by visit with respect to normal ranges and critical values by treatment group.

Table 14.3.2.5 provides a summary of creatinine values at screening and at Days 1, 2, 3, 7, 10, 14, 21, 29, and 90 by treatment group.

9.2.2 Hepatic Safety

The chemistry data will be evaluated for any cases of Hy's Law or Drug Induced Liver Injury (DILI). These were defined as patients with ALT more than 3 X ULN, Total Bilirubin >2 X ULN with a normal Alkaline Phosphatase. Table 14.3.2.6 summarizes these results.

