9.2.11 Clinical Laboratory Assessments

Safety laboratory investigations will include hematology (CBC including platelets and white cell differential), chemistry (Glucose; Electrolytes (Sodium, Potassium, Chloride, Bicarbonate); renal function tests (Urea/BUN, Serum Creatinine); liver function tests (Albumin, Bilirubin Total, Alanine transaminase (ALT), Aspartate transaminase (AST), Alkaline phosphatase (ALP); Total Protein); Calcium; Phosphorus.

CRP (standard test, not high sensitivity-hsCRP) to evaluate inflammatory response will be obtained at Screening and at Days 7, 14 and 29. Spot urine (preferably from first morning void) will be obtained for albumin to creatinine ratio.

Pregnancy testing will be done on all women of childbearing potential participating in the study (using blood test or urine test whichever is faster; blood test only in France).

Clinical laboratory assessments will be collected at intervals according to time and events in Section 18.1.

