3.8 Clinical Laboratory Assessments

Safety laboratory investigations will include results of hematology labs (CBC including platelets and white blood cell differential), and of blood chemistry labs (Glucose; Electrolytes (Sodium, Potassium, Chloride, Bicarbonate, Calcium, Phosphorus); Renal function tests (Urea/BUN, Serum Creatinine); Liver function tests (Albumin, Bilirubin Total, Alanine transaminase (ALT), Aspartate

transaminase (AST), Alkaline phosphatase (ALP); Total Protein). Also, urine albumin / creatine ratio will be evaluated.

Pregnancy testing will be done on all women of childbearing potential participating in the study (using the quicker of a blood test or urine test).

Clinical laboratory assessments will be collected at intervals according to time and events in Section 18.1 of the Clinical Trial Protocol.

Hematology will be collected at Screening, Day 1, Day 3, Day 7, Day 14, and Day 29.

Blood chemistry will be collected at Screening, Day 1 (bilirubin and creatinine only), Day 2 (creatinine only), Day 3 (bilirubin and creatinine only), Day 7, Day 10 (creatinine only), Day 14, Day 21 (creatinine only), Day 29 (albumin and creatinine only), 3 to 21 days after Day 29 visit (creatinine only), and at 3 months (creatinine only). The standard C-Reactive Protein (CRP) test (not the high sensitivity-hsCRP) will be used to evaluate inflammatory response and will be obtained at Screening and Days 7, 14, and 29.

Urine will be collected at Screening, Day 1, Day 3, Day 7, Day 14, Day 29 and Month 3 to measure albumin/creatinine ratio to evaluate renal function and potential injury.

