68	14.3.1.4	Incidence Rates (%) and Event Counts of Drug-Related* TEAEs by System Organ Class and Preferred Term As Treated (Safety) Analysis Set†
69	14.3.1.5	Incidence Rates (%) and Event Counts of Serious TEAEs by System Organ Class and Preferred Term As Treated (Safety) Analysis Set†
70	14.3.1.6	Incidence Rates (%) and Events Counts of Serious TEAEs Sorted by Descending Incidence of Preferred Term in Subjects Receiving Reltecimod As Treated (Safety) Analysis Set†
71	14.3.1.7	Incidence Rates (%) and Events Counts of Serious Drug-Related* TEAEs by System Organ Class and Preferred Term As Treated (Safety) Analysis Set†
71	14.3.1.8	Incidence Rates (%) and Events Counts of Severe TEAEs by System Organ Class and Preferred Term As Treated (Safety) Analysis Set†
72	14.3.1.9	Incidence Rates (%) and Events Counts of Severe TEAEs Sorted by Descending Incidence of Preferred Term in Subjects Receiving Reltecimod As Treated (Safety) Analysis Set†
73	14.3.1.10	Counts of Drug-Related* TEAEs by Severity, System Organ Class, and Preferred Term Reltecimod 0.5 mg/kg As Treated (Safety) Analysis Set†
74	14.3.1.11	Counts of Drug-Related* TEAEs by Severity, System Organ Class, and Preferred Term Placebo As Treated (Safety) Analysis Set†

		Laboratory Data
75	14.3.2.1	Screening, Day 7, Day 14, and Changes from Screening Blood Chemistry by Treatment Group As Treated (Safety) Analysis Set†
76	14.3.2.2	Blood Chemistry Panel Shift Tables Summarizing Changes in Test Status from Screening (Baseline) to Day 7 or Early Discontinuation As Treated (Safety) Analysis Set†
77	14.3.2.3	Blood Chemistry Panel Shift Tables Summarizing Changes in Test Status from Screening (Baseline) to Day 14 or Early Discontinuation As Treated (Safety) Analysis Set†
78	14.3.2.4	Blood Chemistry Frequencies By Visit With Respect To Normal Ranges and Critical Values by Treatment Group As Treated (Safety) Analysis Set†
79	14.3.2.5	Creatinine Values at Screening and at Days 1, 2, 3, 7, 10, 14, 21, 29, and 90 by Treatment Group As Treated (Safety) Analysis Set†
80	14.3.2.6	Summary of Potential Drug Induced Liver Injury (DILI) By Treatment Group As Treated (Safety) Analysis Set†
81	14.3.3.1	Screening, Days 1, 2, 3, 7 and 14, and Changes from Screening Blood Hematology by Treatment Group As Treated (Safety) Analysis Set†
82	14.3.3.2	Blood Hematology Panel Shift Tables Summarizing Changes in Test Status from Screening (Baseline) to Day 7 Early Discontinuation

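### The SAP 9.2.2 liver-injury rule uses ALT only, requires normal ALP and sets no post-dose, baseline or same-visit condition, so Table 14.3.2.6 can count cases present at Screening and omit AST-led or raised-ALP cases

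*SAP*

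**What the plan says.** SAP 9.2.2 (Hepatic Safety) states the task as "The chemistry data will be evaluated for any cases of Hy's Law or Drug Induced Liver Injury (DILI") and gives one definition for both terms: "These were defined as patients with ALT more than 3 X ULN, Total Bilirubin >2 X ULN with a normal Alkaline Phosphatase". The results go to Table 14.3.2.6, listed in SAP Appendix 1 as "Summary of Potential Drug Induced Liver Injury (DILI) By Treatment Group As Treated (Safety) Analysis Set". Neither the section nor the title names a visit window. Protocol 12.12 (Safety Analysis) has no hepatic case rule.

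The liver tests collected are wider than the rule. Protocol 9.2.11 includes "Alanine transaminase (ALT), Aspartate transaminase (AST), Alkaline phosphatase (ALP") alongside total bilirubin in the safety chemistry, and SAP 3.8 repeats the list.

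On timing, SAP 3.8 says: "Blood chemistry will be collected at Screening, Day 1 (bilirubin and creatinine only), Day 2 (creatinine only), Day 3 (bilirubin and creatinine only"), then "Day 7, Day 10 (creatinine only), Day 14, Day 21 (creatinine only), Day 29 (albumin and creatinine only"). SAP 9.2.1 reports values and changes from Screening "for each of 15 tests included in the chemistry panels at Screening, Day 7 and Day 14". It also plans shift tables from Screening to Day 7 and to Day 14 (14.3.2.2 and 14.3.2.3) and by-visit frequencies against normal and critical ranges (14.3.2.4).

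**The concern.** A table labelled as potential drug-induced liver injury should hold events that could follow the drug, and its rule should not pass over the patterns of injury that this population may show. The stated rule falls short in both directions.

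- **Too inclusive on timing.** Nothing limits the search to post-dose values. Adverse events are handled differently: SAP 6.1 requires onset on Day 1 or later and keeps pre-dose events out of the summary tables. Abnormal bilirubin at entry is foreseeable. The SOFA entry score may draw on any of six components (Protocol 6.1, criterion 3), and bilirubin of 2.0 to 5.9 mg/dL alone scores 2 (Protocol Appendix C). The only liver condition named among the exclusions is Child-Pugh class C, with no entry ceiling for ALT, AST or bilirubin.
- **Too exclusive on pattern.** AST is measured but not used. Normal ALP is a condition of being a case, yet patients with a necrotic or gangrenous gallbladder and peritonitis are eligible (Protocol 6.2, criterion 15), and raised ALP is plausible in such patients.

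At stake is whether this table can be read as a count of new liver injury after dosing.

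**Working it through.** The plan gives no case count or rate for this table, so there is no figure to reproduce. The check is a count of visits and a literal application of the rule.

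**Step 1. Visits that can contribute (SAP 3.8).**

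| Test | Scheduled visits | Pre-dose share of visits |
|---|---|---|
| ALT, AST, ALP | Screening, Day 7, Day 14 | 1/3 = 33% |
| Total bilirubin | Screening, Days 1, 3, 7, 14 | 1/5 = 20% |

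All three tests in the rule are scheduled together at three visits, two of them post-dose (Days 7 and 14). No ALT, ALP or bilirubin is scheduled after Day 14. Unscheduled results may add to this, since SAP 6.2.3 provides for unscheduled laboratory pages.

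**Step 2. Effect of having no same-visit rule.** If values from different visits may be paired, the scheduled data allow 3 (ALT) x 5 (bilirubin) x 3 (ALP) = 45 combinations of visits. If all must come from one visit, there are 3. If they must come from one post-dose visit, there are 2. The SAP does not say which applies, so two programmers could follow 9.2.2 and reach different counts.

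**Step 3. The rule applied to four illustrative patients.**

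| Pattern | Outcome under SAP 9.2.2 |
|---|---|
| ALT >3 x ULN, bilirubin >2 x ULN, ALP normal at Screening only | Meets the rule as worded, because no post-dose window excludes it |
| AST >3 x ULN, ALT not above 3 x ULN, bilirubin >2 x ULN, ALP normal at Day 7 | Not a case on any reading |
| ALT >3 x ULN, bilirubin >2 x ULN, ALP raised at Day 7 | Not a case if ALP is judged at that visit; undefined if a normal ALP from another visit may be used |
| ALT >3 x ULN and ALP normal at Day 7, bilirubin >2 x ULN at Day 3 only | Undefined, because there is no same-visit rule |

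The second row follows from a stated limb of the rule and not from missing detail. The third does too, once ALP is read at the qualifying assessment.

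**Step 4. Whether other outputs fill the gap.** Tables 14.3.2.1 to 14.3.2.4 and chemistry listing 16.2.8.19 include AST, ALP and bilirubin. The tables treat each test separately, so they cannot show a patient with both a raised transaminase and raised bilirubin. A shift recorded as high to high hides worsening from a raised baseline. Adverse event tables are a partial backstop: under Protocol 11.1.3 and SAP 6.2.3, laboratory deterioration is to be reported as an adverse event only if it meets a seriousness criterion or leads to stopping treatment, or otherwise at the investigator's discretion. The liver component is also left out of the mSOFA total (SAP 3.7.1 and 5.4).

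**Step 5. Scale.** With 60 patients planned per arm, one misclassified patient moves an arm's rate by 1/60 = 1.7 percentage points. How many would be misclassified is not derivable.

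**The case against.** The strongest reply is that this is a wording gap in one descriptive table with no decision rule attached, and that liver safety is covered elsewhere. The shift tables are conditioned on Screening status, by-visit counts include critical values, treatment-emergent events are tabulated by organ class, chemistry is listed patient by patient, and the iDMC sees unblinded safety data. No drug-related adverse event was found in Phase 1 or 2 and no target organ in animals (Protocol 8.3.1.1), for a single dose with a half-life of about 5 minutes in patients (Protocol 4.1.3.3.2). All of that stands and keeps the point modest. It does not supply a combined criterion.

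A reader might also infer more than the documents support:

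- *That the SAP counts Screening values.* It does not say so. It fails to exclude them, and the term drug-induced could be taken to imply post-dose values.
- *That every patient with raised ALP is dropped.* The SAP does not say at which visit ALP must be normal. The safe statement concerns ALP at the qualifying assessment.
- *That this is the only liver safety output.* It is the only combined one.
- *That an arm difference could not be read.* Pre-dose cases arise before treatment and are balanced in expectation under randomisation. They add noise and dilution, and do not make the table uninterpretable.
- *That a third of cases would be pre-dose.* The 33% is a share of scheduled visits.

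Two further cautions hold. Hepatic SOFA points rest on bilirubin alone, and all patients have Stage 2 or 3 AKI, so entry criteria do not show that anyone meets the full rule at Screening. The normal-ALP limb would also remove some septic Screening cases, so the two faults partly offset.

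**Conclusion.** The concern holds in this form: SAP 9.2.2 states an ALT-only rule with a normal-ALP requirement and sets no post-dose, baseline or same-visit condition. Read literally, Table 14.3.2.6 can include cases already present at Screening, and it omits AST-led cases and cases with raised ALP at the qualifying assessment. No other planned table combines a transaminase with bilirubin.

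The size of the effect is unknown. The documents give no rate of baseline liver abnormality, raised ALP or AST-led injury. The relevance of the ALP limb rests on the assumption that abdominal sepsis raises ALP in some patients. This is a cheap improvement to a safety table. It does not bear on the efficacy analysis, and the documents report no liver signal.

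**What to change.** Reword SAP 9.2.2 and the shell of Table 14.3.2.6 so that:

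1. cases are counted from post-dose values only: the scheduled Day 7 and Day 14 panels plus any unscheduled results;
2. a case is ALT or AST >3 x ULN with total bilirubin >2 x ULN at the same visit;
3. cases with normal ALP and cases with raised ALP at that visit appear in separate rows, which keeps the present definition's ALP condition visible instead of using it to exclude;
4. patients who already met the criterion at Screening are shown in their own row. Mixing them in blurs the count, and dropping them would hide worsening after the dose.

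All variables are already collected. The cost is SAP wording and a few table rows, settled before unblinding. The downside is some less specific flags, for example AST raised by muscle injury in NSTI. The AST threshold is a proposal that mirrors the ALT limb; the documents do not set one.

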9.2.3 Blood Hematology

Similarly, Table 14.3.3.1 summarizes the values and changes from baseline for each of the 15 tests included in the hematology panels at Screening, Day 1, Day 3, Day 7, Day 14, Day 29 by treatment group.

Table 14.3.3.2 provides a shift table summarizing the numbers and percentages of patients going from a normal blood hematology value to a normal, low or high value at Day 7; going from a low baseline blood hematology value to normal, low or high at Day 7; and going from a high baseline blood hematology value to normal, low or high at Day 7. The percentages presented in this table correspond to each baseline status. For example, one of the reported percentages will indicate the percentage of subjects that started with a normal value but ended with a high value. This will be done separately for each treatment group.

Table 14.3.3.3 provides the same information but for shifts to Day 14.

9.3 Urinary Albumin/Creatine Ratio

Table 14.3.4.1 summarizes urinary albumin/creatinine ratio at Screening, Day 1, Day 3, Day 7, Day 14, Day 29 and Month 3 and changes in albumin/creatinine ratio. The measure is used to assess kidney injury and is a marker of CKD.

9.4 Incidence of Chronic Kidney Disease (CKD) at Day 90

Table 14.3.4.2 summarizes the incidence of chronic kidney disease (CKD) at Day 90 in the As Treated (Safety) Analysis Set by treatment group. The definitions provided in [Appendix 8](#) will be used.

9.5 Vital Signs

Baseline height (cm), weight (kg), and BMI (kg/m^2) are summarized for the As Treated (Safety) analysis set in the Demographics and Baseline Disease Characteristics, Table 14.1.2.2.

The following vital sign variables are summarized by treatment group at screening and then at Days 1, 2, 3, 7, 14, 21, and 28 in Table 14.3.5.1. For follow-up visits, changes from screening are also summarized: Weight (kg), Temperature (Celsius), Systolic BP (mmHg), Diastolic BP (mmHg), MAP, Respiratory Rate (breaths/min), and Heart Rate (beats/min).

9.6 Physical Examinations

Results from physical examinations will be provided in the patient listings.

10 Deviations from the Original Statistical Plan

Any deviations from the original statistical plan will be described and justified in the final report.

11 Appendix 1: Tables and Listing TOC

		Enrollment
1	14.1.1.1	Number of Patients by Site Screened and by Analysis Set
2	14.1.1.2	Numbers of Patients by Site, Treatment Group, and Analysis Set
3	14.1.1.3	Number of Patients by Site, Treatment Group, and Randomization Stratum Modified Intent-to-Treat (mITT) Analysis Set
4	14.1.1.4	Number of Patients by Site, Treatment Group, and Randomization Stratum As Treated (Safety) Analysis Set
5	14.1.1.5	Number of Patients by Site, Treatment Group, and Randomization Stratum Per Protocol (PP) Analysis Set
		Demographic and Baseline Characteristics
6	14.1.2.1	Demographics and Baseline Disease Characteristics Overall and By Treatment Group mITT (Randomized and Treated) Analysis Set
7	14.1.2.2	Demographics and Baseline Disease Characteristics Overall and By Treatment Group AT (Safety) Analysis Set
8	14.1.2.3	Demographics and Baseline Disease Characteristics Overall and By Treatment Group Per Protocol Analysis Set
9	14.1.2.4	Demographics and Baseline Disease Characteristics Overall and By Treatment Group Intent-to-Treat Analysis Set
10	14.1.3.1	Patients by Gender and Age Category Overall and by Treatment Group mITT (Randomized and Treated) Analysis Set
11	14.1.3.2	Patients by Gender and Age Category Overall and by Treatment Group AT (Safety) Analysis Set
12	14.1.3.4	Patients by Gender and Age Category Overall and by Treatment Group Per Protocol Analysis Set
		Summary of Baseline Microbiology
13	14.1.3.5	Pathogen (genus / species) in Blood Culture and Tissue Samples in ITT (Randomized) Subjects Overall and By Treatment Group
14	14.1.3.6	Pathogen (genus / species) in Blood Culture Specimens in ITT (Randomized) Subjects Overall and By Treatment Group
15	14.1.3.7	Pathogen (genus / species) in Intra-Abdominal Specimens in ITT (Randomized) Subjects Overall and By Treatment Group

Prior and Concomitant Medications		
16	14.1.4.1	Number (%) of Patients with Prior Non-Antimicrobial Medications or Non-Nephrotoxic Medications by Category and Specific Medication Overall and By Treatment Group As Treated (Safety) Analysis Set
17	14.1.4.2	Number (%) of Patients with Prior Antimicrobial Medications by Category and Specific Medication Overall and By Treatment Group As Treated (Safety) Analysis Set
20	14.1.4.3	Number (%) of Patients with Prior Nephrotoxic Medications by Category and Specific Medication Overall and By Treatment Group As Treated (Safety) Analysis Set
18	14.1.4.4	Number (%) of Patients with Concomitant Non-Antimicrobial Medications or Non-Nephrotoxic Medications by Category and Specific Medication By Treatment Group As Treated (Safety) Analysis Set
19	14.1.4.5	Number (%) of Patients with Concomitant Antimicrobial Medications by Category and Specific Medication By Treatment Group As Treated (Safety) Analysis Set
21	14.1.4.6	Number (%) of Patients with Concomitant Nephrotoxic Medications by Category and Specific Medication By Treatment Group As Treated (Safety) Analysis Set

Medical History		
22	14.1.5.1	Number (%) of Patients Experiencing Prior Medical Conditions During Lifetime by Body System and Specific Medical Condition Overall and By Treatment Group As Treated (Safety) Analysis Set†
23	14.1.5.2	Number (%) of Patients with Ongoing Medical Conditions by Body System and Specific Medical Condition Overall and Treatment Group As Treated (Safety) Analysis Set†
24	14.1.6.1	Number (%) of Patients With Specific Abdominal Infection Presentation Overall and By Treatment Group As Treated (Safety) Analysis Set†
25	14.1.6.2	Number (%) of Patients With Specific Type of Surgical or Interventional Procedure to Establish Source Control Overall and By Treatment Group As Treated (Safety) Analysis Set†
26	14.1.6.3	Number (%) of Patients With AKI Presentation Status As Treated (Safety) Analysis Set†

		Drug Timing and Administration
27	14.1.7.1	Drug Administration and Timing, Overall and By Treatment Group
		Patient Disposition
28	14.1.8.1	Day 29 Study Status by Treatment Group

		Efficacy Analyses
29	14.2.1.1	Numbers and Percentages of Subjects Achieving Freedom from Durable Loss of Renal Function and Improvement in Durable Loss of Renal Function at Day 28 Using LOCF mITT Analysis Set
30	14.2.1.2	Numbers and Percentages of Subjects Achieving Freedom from Durable Loss of Renal Function and Improvement in Durable Loss of Renal Function at Day 28 Using LOCF AT Analysis Set
31	14.2.1.3	Numbers and Percentages of Subjects Achieving Freedom from Durable Loss of Renal Function and Improvement in Durable Loss of Renal Function at Day 28 Using LOCF PP Analysis Set
32	14.2.1.4	Site Variability in Primary Efficacy Endpoint in the mITT Analysis Set
33	14.2.2.1	Numbers and Percentages of Subjects Achieving Secondary Freedom from or Improvement in Durable Loss of Renal Function Endpoints at Days 14, 28, and 90 mITT Analysis Set
34	14.2.2.2	Numbers and Percentages of Subjects Achieving Secondary Freedom from or Improvement in Durable Loss of Renal Function Endpoints at Days 14, 28, and 90 AT (Safety) Analysis Set
36	14.2.2.3	Numbers and Percentages of Subjects Achieving Secondary Freedom from or Improvement in Durable Loss of Renal Function Endpoints at Days 14, 28, and 90 Per Protocol Analysis Set

		SOFA
37	14.2.4.1	Modified SOFA Total Score, Organ Specific Scores, and SOFA Total Score At Screening, Day 1, Day 3, Day 7, and Day 14 By Treatment Group Observed Cases mITT Analysis Set
38	14.2.4.2	Modified SOFA Total Score and Organ Specific Scores Over Time to Day 14 By Treatment Group Last Observation Carried Forward (LOCF) By Treatment Group mITT Analysis Set†
39	14.2.4.3	Modified SOFA Total Score, Organ Specific Scores, and SOFA Total Score At Screening and Changes from Screening to Day 1, Day 3, Day 7, and Day 14 By Treatment Group Observed Cases mITT Analysis Set†
40	14.2.4.4	Modified SOFA Total Score, Organ Specific Scores, and SOFA Total Score At Screening and Changes from Screening to Day 1, Day 3, Day 7, and Day 14 By Treatment Group Last Observation Carried Forward (LOCF) mITT Analysis Set†
41	14.2.4.5	Resolution of Organ Dysfunction to Days 14 Overall and by Individual Organ By Treatment Group mITT Analysis Set
42	14.2.4.6	Resolution of Organ Dysfunction to Days 14 Overall and by Individual Organ By Treatment Group mITT Analysis Set Among Subjects Presenting with Shock
43	14.2.4.7	Resolution of Organ Dysfunction to Days 14 Overall and by Individual Organ By Treatment Group PP Analysis Set
44	14.2.4.8	Resolution of Organ Dysfunction to Days 14 Overall and by Individual Organ By Treatment Group PP Analysis Set Among Subjects Presenting with Shock

Critical Care		
45	14.2.5.1	Critical Care and Hospital Stay Parameters Over Days 1 to 28 By Treatment Group mITT Analysis Set†
46	14.2.5.2	Hospital Discharge Status By Treatment Group mITT Analysis Set
47	14.2.5.3	Hospital Readmissions By Treatment Group mITT Analysis Set
48	14.2.5.4	Critical Care and Hospital Stay Parameters Over Days 1 to 28 By Primary Effectiveness Endpoint* Success vs. Failure mITT Analysis Set
49	14.2.5.5	Critical Care and Hospital Stay Parameters Over Days 1 to 28 Comparing Subjects with Day 14 mSOFA \leq 1 to Day 14 mSOFA \geq 2 mITT Analysis Set
50	14.2.5.6	Critical Care and Hospital Stay Parameters Over Days 1 to 28 By Treatment Group PP Analysis Set†
51	14.2.5.7	Critical Care and Hospital Stay Parameters Over Days 1 to 28 By Treatment Group mITT Analysis Set† Alive at Day 14
52	14.2.5.8	Critical Care and Hospital Stay Parameters Over Days 1 to 28 By Treatment Group PP Analysis Set Alive at Day 14†

Survival and Time-to-Event Analyses		
53	14.2.6.1	Life Table Analysis to Day 90 Mortality – Reltecimod 0.5 mg/kg mITT Analysis Set
54	14.2.6.2	Life Table Analysis to Day 90 Mortality – Placebo mITT Analysis Set
55	14.2.6.3	Life Table Analysis to Day 90 Mortality – Subjects with Freedom from Durable Loss of Renal Function at Day 28 mITT Analysis Set – Reltecimod 0.5 mg/kg
56	14.2.6.4	Life Table Analysis to Day 90 Mortality – Subjects with Freedom from Durable Loss of Renal Function at Day 28 mITT Analysis Set – Placebo
57	14.2.6.5	Life Table Analysis to Day 90 Mortality – Subjects with Freedom from Durable Loss of Renal Function at Day 28 mITT Analysis Set – All
58	14.2.6.6	Life Table Analysis to Day 90 Mortality – Reltecimod 0.5 mg/kg PP Analysis Set
59	14.2.6.7	Life Table Analysis to Day 90 Mortality – Placebo PP Analysis Set
60	14.2.6.8	Life Table Analysis to Day 90 Mortality – Reltecimod 0.5 mg/kg mITT Analysis Set in Subjects Presenting with Shock
61	14.2.6.8	Life Table Analysis to Day 90 Mortality - Placebo mITT Analysis Set in Subjects Presenting with Shock
62	14.2.6.8	Life Table Analysis to Day 90 Mortality – Day 14 mSOFA ≤ 1 mITT Analysis Set
63	14.2.6.8	Life Table Analysis to Day 90 Mortality – Day 14 mSOFA ≥ 2 mITT Analysis Set
		C-Reactive Protein
64	4.2.7.1	C-Reactive Protein at Screening and at Days 7, 14, and 29 and Changes from Screening by Treatment Group mITT Analysis Set†

		Adverse Events
65	14.3.1.1	Summary of Treatment-Emergent Adverse Events (TEAEs) By Treatment Group As Treated (Safety) Analysis Set†
66	14.3.1.2	Incidence Rates (%) and Event Counts of TEAEs by System Organ Class and Preferred Term By Treatment Group As Treated (Safety) Analysis Set†
67	14.3.1.3	Incidence Rates (%) and Event Counts of TEAEs Sorted by Descending Incidence of Preferred Term As Treated (Safety) Analysis Set†
68	14.3.1.4	Incidence Rates (%) and Event Counts of Drug-Related* TEAEs by System Organ Class and Preferred Term As Treated (Safety) Analysis Set†
69	14.3.1.5	Incidence Rates (%) and Event Counts of Serious TEAEs by System Organ Class and Preferred Term As Treated (Safety) Analysis Set†
70	14.3.1.6	Incidence Rates (%) and Events Counts of Serious TEAEs Sorted by Descending Incidence of Preferred Term in Subjects Receiving Reltecimod As Treated (Safety) Analysis Set†
71	14.3.1.7	Incidence Rates (%) and Events Counts of Serious Drug-Related* TEAEs by System Organ Class and Preferred Term As Treated (Safety) Analysis Set†
71	14.3.1.8	Incidence Rates (%) and Events Counts of Severe TEAEs by System Organ Class and Preferred Term As Treated (Safety) Analysis Set†
72	14.3.1.9	Incidence Rates (%) and Events Counts of Severe TEAEs Sorted by Descending Incidence of Preferred Term in Subjects Receiving Reltecimod As Treated (Safety) Analysis Set†
73	14.3.1.10	Counts of Drug-Related* TEAEs by Severity, System Organ Class, and Preferred Term Reltecimod 0.5 mg/kg As Treated (Safety) Analysis Set†
74	14.3.1.11	Counts of Drug-Related* TEAEs by Severity, System Organ Class, and Preferred Term Placebo As Treated (Safety) Analysis Set†

		Laboratory Data
75	14.3.2.1	Screening, Day 7, Day 14, and Changes from Screening Blood Chemistry by Treatment Group As Treated (Safety) Analysis Set†
76	14.3.2.2	Blood Chemistry Panel Shift Tables Summarizing Changes in Test Status from Screening (Baseline) to Day 7 or Early Discontinuation As Treated (Safety) Analysis Set†
77	14.3.2.3	Blood Chemistry Panel Shift Tables Summarizing Changes in Test Status from Screening (Baseline) to Day 14 or Early Discontinuation As Treated (Safety) Analysis Set†
78	14.3.2.4	Blood Chemistry Frequencies By Visit With Respect To Normal Ranges and Critical Values by Treatment Group As Treated (Safety) Analysis Set†
79	14.3.2.5	Creatinine Values at Screening and at Days 1, 2, 3, 7, 10, 14, 21, 29, and 90 by Treatment Group As Treated (Safety) Analysis Set†
80	14.3.2.6	Summary of Potential Drug Induced Liver Injury (DILI) By Treatment Group As Treated (Safety) Analysis Set†
81	14.3.3.1	Screening, Days 1, 2, 3, 7 and 14, and Changes from Screening Blood Hematology by Treatment Group As Treated (Safety) Analysis Set†
82	14.3.3.2	Blood Hematology Panel Shift Tables Summarizing Changes in Test Status from Screening (Baseline) to Day 7 Early Discontinuation
83	14.3.3.3	Blood Hematology Panel Shift Tables Summarizing Changes in Test Status from Screening (Baseline) to Day 14 Early Discontinuation
84	14.3.3.4	Blood Hematology Frequencies by Visit with Respect to Normal Ranges and Critical Values by Treatment Group As Treated (Safety) Analysis Set

85	14.3.4.1	Screening, Days 1, 3, 7, 14, 29 and 29 and Changes from Screening Urinary albumin/creatinine ratio by Treatment Group As Treated (Safety) Analysis Set†
86	14.3.4.2	Incidence of chronic kidney disease (CKD) at Day 90 by Treatment Group As Treated (Safety) Analysis Set†
		Vital Signs
87	14.3.5.1	Vital Signs at Screening, Day 1, Day 2, Day 3, Day 7, Day 14, Day 21, Day 29 and Changes from Screening By Treatment Group As Treated (Safety) Analysis Set†

12 Appendix 2: AE Listings

		AE Listings
1	16.2.7.1	All TEAEs Sorted by Specific AE by Treatment Group, Sorted by SOC and PT As Treated (Safety) Analysis Set
2	16.2.7.2	All TEAEs Sorted by Specific AE by Treatment Group, Sorted by Patient ID and Onset As Treated (Safety) Analysis Set
3	16.2.7.3	Drug-Related TEAEs Sorted by Specific AE by Treatment Group, Sorted by SOC and PT As Treated (Safety) Analysis Set
4	16.2.7.4	Serious TEAEs Sorted by Specific AE + by Treatment Group, Sorted by SOC and PT As Treated (Safety) Analysis Set
5	16.2.7.5	Serious Drug-Related TEAEs Sorted by Specific AE by Treatment Group, Sorted by SOC and PT As Treated (Safety) Analysis Set
6	16.2.7.6	All TEAEs with Outcome of Death Sorted by Specific AE by Treatment Group, Sorted by SOC and PT As Treated (Safety) Analysis Set
7	16.2.7.7	All TEAEs with Outcome of Drug-Related Death Sorted by Specific AE by Treatment Group, Sorted by SOC and PT As Treated (Safety) Analysis Set
8	16.2.7.8	All TEAEs with Outcome of Study Drug Discontinuation Sorted by Treatment Group, SOC, and PT As Treated (Safety) Analysis Set
9	16.2.7.9	All TEAEs with Outcome of Discontinuation from Study Sorted by Treatment Group, SOC, and PT As Treated (Safety) Analysis Set
10	16.2.7.10	Day 0 AE's Sorted by SOC and PT As Treated (Safety) Analysis Set

13 Appendix 3: Patient Listings

		Patient Listings
	16.2.8.1	Form: Randomization and Administration
	16.2.8.2	Form: Demographics
	16.2.8.3	Form: Abdominal Sepsis
	16.2.8.4	Form: Abdominal Sepsis Information
	16.2.8.5	Form: Primary Infection Site Assessment
	16.2.8.6	Form: Initial Source Control
	16.2.8.7	Form: Follow-Up Source Control
	16.2.8.8	Form Acute Kidney Injury
	16.2.8.9	Form: Inclusion/Exclusion
